### 5.3 Efficacy Evaluation

#### Analysis of Primary Endpoint

A multilevel model incorporating the participants as a random term is applied to the repeated measures in the same participant, including the factor group and the baseline value as a covariate. The primary analysis is performed within the framework of this model as an ANCOVA of the PHQ-9 change scores (T0 to T3-difference), with subsequent pairwise comparisons of interventions by test of the corresponding contrasts. The primary analysis is performed in the respective FAS population. The pairwise comparisons are done if the global test of group ( $H_0$ : all means are equal) could be rejected. Each test will be performed at a two-sided level of alpha = 0.05. This closed testing principle will ensure a family-wise error level of 5%.

Absolute, and relative frequencies of missing observations are presented both overall and separately for the randomized groups.

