### 1.3 Study Endpoint(s)

#### 1.3.1 Primary Endpoint

The primary endpoint of the study is the change in self-reported depression severity total score from baseline to six months after randomization, measured via the Patient Health Questionnaire-9 (PHQ-9; Kroenke et al., 2001; Löwe et al., 2004). The PHQ-9 consists of 9 items and is scored on a 4-point Likert scale (0–3), resulting in a total score ranging from 0 to 27 (0 = best, 27 = worst).

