### 3.3 Analysis Populations

#### Full Analysis Set (FAS)

The primary analysis is based on the full analysis set (FAS). It is as complete as possible and as close as possible to the Intention-To-Treat (ITT) principle which includes all randomized participants, as belonging to their randomization arm, regardless of whether they received the feedback or not, or whether other protocol violations are known. For the FAS at least a valid baseline and one valid post-baseline value of the primary outcome needs to be available.

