## 5.2 Missing Data

The multilevel modelling approach limits the bias when handling missing data even in the case of not missing at random (NMAR).

As a sensitivity analysis missing values are imputed by different approaches for the primary analysis. In the FAS population no baseline value is missing as per definition. In case of missing follow-up values,

we conduct last observation carried forward (LOCF) and multiple imputation. In the LOCF approach, missing values are replaced by the previous valid value. The imputation model in the multiple imputation approach includes all baseline characteristics of participants and all variables of the primary outcome analysis. From the baseline values of the secondary outcomes, we include as many variables in the imputation model as possible. For the imputation of missing follow-up values, 100 imputed data sets are generated, and the results are combined using Rubin's Rules.

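### The primary PHQ-9 model is worded as repeated measures but has no time or group-by-time term, and section 5.2's missing-data rationale does not cover the T3-only ANCOVA it more naturally describes

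*SAP*

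**What the plan says.** **Endpoint.** Section 1.3.1: "The primary endpoint of the study is the change in self-reported depression severity total score from baseline to six months after randomization". Section 5.1 defines it as T3 minus T0.

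**Primary model.** Section 5.3, Analysis of Primary Endpoint, sets up a multilevel model with participant as a random term, "applied to the repeated measures in the same participant, including the factor group and the baseline value as a covariate". It then says that, within this framework, the primary analysis is done "as an ANCOVA of the PHQ-9 change scores (T0 to T3-difference"), followed by pairwise contrasts if the global group test rejects. Of the population it says: "The primary analysis is performed in the respective FAS population".

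**Population.** Section 3.3: "For the FAS at least a valid baseline and one valid post-baseline value of the primary outcome needs to be available". Table 1 in section 2.6 schedules the PHQ-9 at T0, T2 and T3.

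**Missing data.** Section 5.2: "The multilevel modelling approach limits the bias when handling missing data even in the case of not missing at random (NMAR"). It continues: "As a sensitivity analysis missing values are imputed by different approaches for the primary analysis". On LOCF: "In the LOCF approach, missing values are replaced by the previous valid value".

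**Where time is named.** The secondary-endpoint model in section 5.3 includes time point and group-by-time, and drops the interaction if it is not significant. Through section 5.1 that model covers PHQ-9 change at T2 and T3, as an exploratory analysis. The further PHQ-9 model under Sensitivity Analyses has time point and no interaction. The primary model has neither term.

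**The concern.** The endpoint is clear, but the description of the model does not lead to one fit. A random participant term on repeated measures needs more than one row per participant. Once T2 and T3 rows both enter, an effect at T3 needs time and group-by-time, and the text lists neither. If only the T3 change enters, the repeated-measures wording does no work, and the analysis is a complete-case ANCOVA at T3.

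Three things are at stake. The analyst must either ignore part of the text or add unlisted terms in the only confirmatory test. On the T3-only reading, T2 scores already collected go unused in that test. And the plan then credits its primary analysis with protection against missing data that this analysis does not have, although section 2.3 allows for 35% dropout.

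**Working it through.** **1. The plan's own figure.** From section 2.3: f = 0.118, three groups, alpha 0.05, 233 per group. Noncentrality = N × f² = 699 × 0.118² = 9.73. The F test on 2 and 695 df has power 80.2%, so the figure is reproduced. Dropout: 233 / 0.65 = 358.5 (plan: 358). If two arms are equal and one differs, f = 0.118 means a difference of 0.118 × 3 / √2 = 0.25 SD. None of this is disputed.

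**2. Assumptions.** The SAP gives neither the T2-T3 correlation nor the share with T2 only. I take r = 0.3, 0.5 and 0.7. In each arm, p3 = 65% have both visits (from the 35% dropout) and 15% have T2 only (range 5-25%), so p2 = 80%. Effects are in SD of PHQ-9 change.

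**3. Reading A: T2 and T3 rows with the listed terms.** One group coefficient averages the two visits. Per participant randomised, V2 = 1/p2, C = r/p2 and V3 = (1 − r²)/p3 + r²/p2. The weight on T3 is (V2 − C)/(V2 + V3 − 2C).

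- At r = 0.5: V2 = 1.25, C = 0.625, V3 = 1.466, weight = 0.625/1.466 = 0.426.
- At r = 0.3 and 0.7 the weight is 0.435 and 0.418.
- A true effect of 0.25 at T3 and none at T2 is therefore estimated as 0.10-0.11.

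The formula is for group plus time, which is the sensitivity model in section 5.3. In a simulation (1,500 runs, residual SD 5 points, r = 0.6, everyone seen at T2, 35% missing T3 at random), a true T3 effect of −1.25 with no T2 effect came out as −0.44 both with and without the time term. With group-by-time, the T3 contrast was −1.24. If the effect is the same at both visits, pooling does no harm (−1.25 returned).

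**4. Reading B: T3 change only.** With one row per participant, the likelihood depends only on the sum of the participant and residual variances, so the random term cannot be estimated. T2-only members are unused:

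| T2 only | Unused / FAS |
|---|---|
| 0% (FAS requires T3) | 0 |
| 5% | 54 / 752 (7%) |
| 15% | 161 / 859 (19%) |
| 25% | 269 / 967 (28%) |

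Counts are 1074 × share over 1074 × (0.65 + share).

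**5. Precision lost on Reading B.** The variance of the T3 mean with group-by-time, relative to T3-only, is (1 − r²) + r² × p3/p2. At 15% and r = 0.5 it is 0.75 + 0.25 × 0.8125 = 0.953.

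| T2 only | Ratio, r = 0.3 / 0.5 / 0.7 | Power |
|---|---|---|
| 5% | 0.994 / 0.982 / 0.965 | 80.5 / 81.0 / 81.7% |
| 15% | 0.983 / 0.953 / 0.908 | 81.0 / 82.2 / 84.1% |
| 25% | 0.975 / 0.931 / 0.864 | 81.3 / 83.2 / 86.0% |

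**6. Bias on Reading B.** Let return at T3 be logistic in the T2 score, in one arm only, with 65/80 = 81.25% returning. The returners' mean T2 score shifts by 0.066 SD at odds ratio 0.70 per SD, and by 0.121 SD at 0.50. The T3-only bias is r times the shift: 0.020 / 0.033 / 0.046 and 0.036 / 0.061 / 0.085. The group-by-time model is within 0.002 of zero. With equal dependence in all arms, the T3-only bias is at most 0.009.

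**7. The NMAR claim, with T2 in the model.** Same setting, one arm, odds ratio 0.50:

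| Return depends on | T3-only bias | Group-by-time bias |
|---|---|---|
| T3 score | 0.121 | 0.121 × (1 − r²) = 0.110 / 0.091 / 0.062 |
| T3 minus T2 | 0.121 × √((1 − r)/2) = 0.072 / 0.061 / 0.047 | (1 + r) times that = 0.093 / 0.091 / 0.080 |

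The repeated-measures model lowers the bias in the first case and raises it in the second. Limiting bias under NMAR is thus not a general property of it.

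**The case against.** The strongest reply is that the primary test is less open than its wording suggests. Section 5.3 names an ANCOVA of the T3 change, section 2.3 powers a one-way ANCOVA on 233 per group after dropout, and sections 1.3.1 and 5.1 fix T3. I accept this: the T3-only ANCOVA is the more natural reading and a legitimate primary analysis. What remains is wording about repeated measures that it cannot use, and a rationale in section 5.2 that does not apply to it.

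Second, section 3.3 asks for a post-baseline value of the primary outcome, and the Table 1 footnote marks only T3 as primary. On that reading there are no T2-only members. Against it, section 5.2 imputes missing follow-up values for the primary analysis in the FAS, and LOCF carries forward a previous value. If every FAS member had T3, no T3 change would be missing. The T2-only group is therefore a well-founded inference, but the text does not settle it.

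A reader might go further than the documents allow:

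- *The SAP never plans a PHQ-9 model with group-by-time.* It does, in the secondary analysis, though as exploratory and with the interaction removable.
- *T2-only participants are lost altogether.* LOCF and multiple imputation bring them in, as sensitivity analyses. The imputation list does not name the T2 PHQ-9. It is covered only if the variables of the primary analysis include it, which they do not on the T3-only reading.
- *The primary result will be materially biased.* That needs dropout that depends on T2 differently by arm, and nothing in the SAP shows this.
- *The sensitivity model's averaging over visits undermines the confirmatory test.* It does not. It only means that this model does not check the T3 effect.

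**Conclusion.** The point stands as a defect of specification that should be fixed. The listed terms do not give a T3 contrast from repeated measures. The T3-only ANCOVA that the text more naturally describes cannot use the random term or any T2-only FAS member, and does not inherit the protection that section 5.2 claims. The NMAR part of that claim is too strong for either model.

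The consequences for the result are modest. Power would be about 80-86% instead of 80%. T3-only bias is at most 0.01 SD with equal dependence across arms, and 0.02-0.09 SD if return depends on the T2 score in one arm only. These figures rest on assumed correlations, T2-only shares and return mechanisms. If the FAS requires T3, the number unused is 0 and only the mismatch of wording and rationale remains. The endpoint and the sample size of 233 (358 recruited) per group are not in question.

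**What to change.** **Preferred.**

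- *Section 5.3, primary analysis:* model PHQ-9 change at T2 and T3 with group, time, group-by-time (kept whatever its p-value), baseline PHQ-9 and a stated within-participant covariance, for example unstructured. Take the 2-df global test and the pairwise contrasts at T3, in all FAS members.
- *Section 5.3, sensitivity analyses:* make the T3-only ANCOVA a sensitivity analysis, in place of the group-plus-time model.
- *Section 5.2:* limit the claim to data missing at random given the observed PHQ-9 scores, and name the T2 PHQ-9 in the imputation model.
- *Section 3.3:* state that either T2 or T3 counts as the post-baseline value.

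**Alternative.** Keep the T3-only ANCOVA as primary. Delete the repeated-measures and random-term wording, state that the fit uses only FAS members with a T3 value, and remove the section 5.2 rationale for it.

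**Cost.** SAP wording and a few lines of SAS. The T2 PHQ-9 is already collected, and the extra parameters are negligible at this sample size. The preferred model still relies on data missing at random, and cannot help participants with neither T2 nor T3.

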#### Analysis of Secondary Endpoints

The secondary endpoint analyses are performed in the respective FAS population. All secondary endpoints are compared and statistically assessed for descriptive purposes and not in a confirmatory sense. The aim of the analysis is an exploratory data analysis, not hypothesis testing or generation of evidence for the efficacy. No attempt is made to adjust for the p-values for multiple testing.

Mean, standard deviation, first and third quartile, minimum and maximum for the continuous variables and absolute and relative frequencies for the categorical and binary variables are presented both overall and separately for the randomized groups for each time point. Number of missing observations are presented for the randomized groups separately for each time point. All summary tables are structured with a column for each group (tailored feedback, standard feedback, no feedback) and a total column.

Multilevel linear models with differences from baseline as outcome, incorporating the participants as a random term, are applied to the repeated measures in the same participant, including the factor group, time point, and the baseline value as a covariate. The interaction between time and the group is determined. If it is not significant, it is eliminated from the model. Adjusted means with 95% confidence intervals (CI) and p-values are reported.

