### 2.3 Sample Size

Based on the results of the preceding DEPSCREEN-INFO trial (Löwe et al., 2016), the study is powered to detect a small mean difference (Cohen's  $f = 0.118$ ) in the primary outcome (depression severity) in any pairwise comparison between all three study arms. The calculation is based on a global one-way ANCOVA adjusted for baseline depression severity, with an alpha of 0.05 (two-sided) and a power of 80%. It results in a needed sample size of  $n = 233$  participants per group (PASS, 2008). To allow for an estimated drop out of 35% (c.f. Christensen et al., 2009), 358 participants per group are recruited (1074 in total).

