#### Sensitivity Analyses

The primary endpoint analysis is repeated within the PP population.

Further for the primary endpoint a multilevel linear model with change from baseline as outcome incorporating the participants as a random term are applied to the repeated measures in the same

participant, including the factor group, time point, and the baseline value as a covariate. Adjusted means with 95% CI and p-values are reported.

See section 5.2 for sensitivity analyses regarding missing value imputation.

In addition, a subgroup analysis regarding the baseline depression severity (moderate: PHQ-9  $\geq 10$  and  $\leq 14$  points; severe: PHQ-9  $\geq 15$  points) is planned. The model defined for the primary analysis of the PHQ-9 change score will be extended by the factor depression severity (moderate / severe). The interaction of the feedback-group and the depression severity will be investigated. In case the p-value of the interaction is  $< 0.05$  we consider that the depression severity at baseline is influencing the PHQ-9 effect.

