## 5.5 Additional Analyses

### Check of Assumptions

#### Normality of residuals and linearity

The assumptions regarding normality of residuals, and linearity between the independent variables and the dependent variable are examined graphically. Partial residual plots are used to examine linearity. Residual plots and quantile-quantile plots are used to evaluate normality of residuals. In case of unmet assumptions, the Box-Cox transformation is applied in order to find out which power transformation is reasonable in terms of not violating the assumption.

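### The joint 1-month and 6-month models name only a participant random term, which as usually fitted gives both visits one variance, so visit-specific standard errors are off if the spreads differ

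*SAP*

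**What the plan says.** Three parts of SAP 5.3 describe the within-participant structure, all in the same limited way.

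- **Secondary endpoints:** "Multilevel linear models with differences from baseline as outcome, incorporating the participants as a random term, are applied to the repeated measures". The terms are group, time point and baseline. A group-by-time interaction is examined and removed if not significant. The status is exploratory: "All secondary endpoints are compared and statistically assessed for descriptive purposes and not in a confirmatory sense". Other endpoints, including the Brief IPQ items, follow the same approach.
- **Sensitivity analyses of the primary endpoint:** "a multilevel linear model with change from baseline as outcome incorporating the participants as a random term", with group, time point and baseline. No interaction is named.
- **Primary endpoint:** a multilevel model with a participant random term on repeated measures, with group and baseline. The test itself is described as an ANCOVA on the T0 to T3 change. "Each test will be performed at a two-sided level of alpha = 0.05", and "This closed testing principle will ensure a family-wise error level of 5" per cent.

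No section names a residual covariance structure, visit-specific variances or robust standard errors. On assumption checks, 5.5 says: "The assumptions regarding normality of residuals, and linearity between the independent variables and the dependent variable are examined graphically".

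By Table 1 (2.6), only PHQ-9 and Brief IPQ are measured at both T2 and T3. GAD-7, SSS-8 and EQ-5D-5L have one follow-up value each, so the point does not touch them.

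**The concern.** A random participant term plus one residual variance gives every visit the same total variance. Change scores one month and six months after a common baseline need not have equal spread. If the correlation with baseline weakens over time, the variance left after baseline adjustment is larger at T3 than at T2. The model then averages the two variances. The T3 contrast gets a standard error that is too small and the T2 contrast one that is too large, or the reverse if spread shrinks.

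At stake are the intervals and p-values of the visit-specific PHQ-9 results (including the 1-month secondary endpoint) and of the Brief IPQ items. If the primary 6-month contrast were drawn from such a model, the size of the confirmatory test would be at stake too. Equality of variance across visits is not among the assumptions that 5.5 lists, and no remedy for unequal variance is given.

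**Working it through.** **Inputs from the SAP.** Two-sided alpha 0.05 (5.3); three arms, 1:1:1 (2.1); 233 evaluable and 358 recruited per group (2.3).

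**The plan's own figure.** In 2.3, "the study is powered to detect a small mean difference" (Cohen's f = 0.118) "with an alpha of 0.05 (two-sided) and a power of 80" per cent. A noncentral F calculation with three groups and one covariate (noncentrality N x f², df 2 and N - 4) needs 232 per group and gives 80.2% power at 233. Allowing for 35% dropout, 233/0.65 = 358.5, against 358 stated. The sample size reproduces; it involves no visit-specific variance.

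**Assumption, not in the SAP.** r = residual SD at T3 / residual SD at T2, after baseline adjustment. For illustration, with equal marginal SDs and a correlation with baseline of 0.6 at one month falling to 0.5 or 0.4 at six months, r = sqrt(1 - 0.25)/sqrt(1 - 0.36) = 1.08, or sqrt(1 - 0.16)/sqrt(1 - 0.36) = 1.15.

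**Formulas** (complete data, model with group-by-time, T2 SD set to 1). Compound symmetry uses the average variance (1 + r²)/2 at both visits. Hence:

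- T3: model SE / true SE = sqrt(q), with q = (1 + r²)/(2r²)
- T2: model SE / true SE = sqrt((1 + r²)/2)
- Global T3 test (2 df): size = P(chi-square > 5.99q) = exp(-2.996q)
- One pairwise T3 test: size = 2(1 - Φ(1.96 sqrt(q)))

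| r | q | T3 SE ratio | T2 SE ratio | Global size | Pairwise size |
|---|---|---|---|---|---|
| 0.9 | 1.117 | 1.06 | 0.95 | 3.5% | 3.8% |
| 1.0 | 1.000 | 1.00 | 1.00 | 5.0% | 5.0% |
| 1.1 | 0.913 | 0.96 | 1.05 | 6.5% | 6.1% |
| 1.2 | 0.847 | 0.92 | 1.10 | 7.9% | 7.1% |

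**Simulation check** (REML, null hypothesis, T2-T3 correlation 0.5, 6,000 trials per setting). Two patterns per arm were used: 233 complete, or 213 with both visits, 60 with T2 only and 20 with T3 only. Global T3 test size was 6.6% and 6.7% at r = 1.1, and 8.0% and 7.8% at r = 1.2. Family-wise error of the gated procedure was the same.

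**Which models are affected:**

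- *Group effect averaged over visits (no interaction), participant random term:* global error 4.5% at r = 1.2 and 5.3% at r = 1.5. A second simulation used 358 per arm, 25% missing at T2, 35% at T3, correlation 0.55 and 4,000 trials. For r from 1 to 1.5 it gave 4.6 to 5.8% for the primary model's listed terms and 5.0 to 5.8% for the sensitivity model's, without a trend in r. With an interaction added, the T3 contrast in the same setting reached 8.5% at r = 1.2.
- *ANCOVA of the T3 change alone:* 5.3% at r = 1.2 and 4.8% at r = 1.5.
- *Joint model, T3 contrast, unstructured covariance:* 4.9% at r = 1.2 and 5.0% at r = 1.5 (2,000 trials).

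The distortion therefore needs three things together: both visits in one model, a visit-specific contrast, and a single variance.

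**The case against.** A reader might infer that the plan's confirmatory 5% level is broken. The text does not support that. The primary analysis names neither time point nor interaction and describes an ANCOVA on the T0 to T3 change. Read as T3-only, each participant has one value and there is no variance to share across visits. Read as pooling T2 and T3 rows, the group effect is an average over visits and its size stays near 5%. The sensitivity model as listed is in the same position. That an averaged effect is not a 6-month effect is a separate matter.

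Nor does the plan force equal variances. It leaves the residual structure unstated, and residuals that differ by visit are compatible with its wording. The value and direction of r are assumed. The secondary analyses claim no error control, and once the interaction is dropped they contain no separate T2 and T3 contrasts. Unequal spread could also be noticed, since 5.5 calls for residual plots and 5.3 for standard deviations at each time point.

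All of this stands. It does not remove the gap. The only structure named is one whose usual implementation assumes equal variance, and no response is planned if that fails. The primary reading is also not settled. A participant random term on repeated measures makes little sense with one row per participant. The FAS (3.3) admits participants with any one post-baseline PHQ-9, and 5.2 relies on the multilevel model for missing data. Those statements point towards T2 data entering the primary model, while the ANCOVA wording and the separately listed longitudinal sensitivity model point the other way.

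**Conclusion.** The point holds for joint T2/T3 models that yield visit-specific estimates: PHQ-9 and Brief IPQ when the interaction is retained, and the sensitivity or primary model only if T2 rows enter and a 6-month contrast is drawn. Implemented with a single residual, such models misstate the T3 standard error by 4 to 8% (too small) at r = 1.1 to 1.2, or by about 6% (too large) at r = 0.9, with the opposite error at T2. These sizes rest on an SD ratio that the SAP does not give and on complete-data algebra that simulation supports. The confirmatory family-wise level would be at risk only under a joint primary model with group-by-time. No breach of it is shown. This is a low-cost improvement, mainly to exploratory intervals and p-values.

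**What to change.** 1. In every joint T2/T3 model that yields visit-specific estimates, replace the participant random term with an unstructured 2x2 within-participant residual covariance, fitted by REML, and let the baseline coefficient differ by time point.
2. In Analysis of Primary Endpoint, state whether T2 data enter the primary model. If they do, use the same covariance with group-by-time and take the 6-month contrast from it. If they do not, call the test a T3-only ANCOVA and drop the random term.

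The cost is a sentence in each place, one changed line of SAS code, one extra covariance parameter and one extra baseline coefficient. With several hundred participants per arm the loss is negligible if the variances are in fact equal: at r = 1, over 1,500 simulated null trials, the global test size was 4.3% with unstructured covariance and 4.4% with the random term.

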#### 1.3.2 Secondary endpoints

- PHQ-9 total score change from baseline to one month after randomization.
- Depression diagnosis by a health care professional, resulting in a binary variable (yes / no), measured by self-report 6 months after randomization.
- Guideline-based depression care, using a self-developed questionnaire (psychotherapy and/or medication), based on the German National Clinical Practice Guideline for Unipolar Depression (DGPPN et al., 2015), resulting in a binary variable (yes / no), measured 6 months after randomization.

- Depression-related health behaviour, using a self-developed questionnaire (information-seeking, seeking social support, self-management, seeking formal help), resulting in a binary variable (yes / no), 6 months after randomization.
- Health-related quality of life will be assessed using the EuroQol-5D (EQ-5D-5L, Ludwig et al., 2018) six months after randomization, change from baseline. The EuroQol-5D index-value is generated using 5 dimensions: mobility, self-care, activity, pain and anxiety (each on a 5-point scale: 1 = best, 5 = worst). In addition, a visual analogue scale (VAS) is assessed.
- Anxiety severity measured via the 7-item Generalized Anxiety Disorder total score change (GAD-7, Spitzer et al., 2006, German version: Löwe et al., 2008) six months after randomization, change from baseline.
- Somatic symptom severity measured via the 8-item Somatic Symptom Scale total score (SSS-8, Gierk et al., 2014) six months after randomization, change from baseline.

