### Secondary Outcome

The following secondary endpoints are continuous outcomes. For these, difference from baseline (T0) is calculated for 1 month (T2; PHQ-9 only) and 6 months after randomization (T3, all outcomes):

- PHQ-9 total score (9 items)
- GAD-7 total score (7 items)
- SSS-8 total score (8 items)
- EQ-5D-5L (index-value, VAS)

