### Other Outcomes

The following other endpoints are continuous outcomes:

- Brief IPQ single items (difference from baseline (T0) is calculated for 1 month (T2) and 6 months after randomization (T3))
- Critical life events at T3 (sum score for positive and negative life events, respectively)

The following other endpoints are binary outcomes. For these, no difference to baseline (T0) is calculated:

- SCID at T1 and T3

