#### Analysis of other Endpoints

Other endpoints will be analysed, depending on the level of scale, as defined for the secondary endpoints. See chapter 5.3. The SCID will be analysed descriptively using summary statistics.

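### Dropping a non-significant time-by-group term leaves the listed one-month PHQ-9 endpoint with a pooled one- and six-month contrast, whose 95% interval can under-cover

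*SAP*

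**What the plan says.** SAP section 1.3.2 gives "PHQ-9 total score change from baseline to one month after randomization" its own bullet among the secondary endpoints. Section 5.1, Secondary Outcome, fixes the time points: "For these, difference from baseline (T0) is calculated for 1 month (T2; PHQ-9 only) and 6 months after randomization (T3, all outcomes". PHQ-9 is therefore the only continuous secondary outcome with data at both T2 and T3.

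Section 5.3, Analysis of Secondary Endpoints, fits a multilevel linear model to the changes from baseline, with group, time point and baseline value as terms and participant as a random term. It then applies this rule: "The interaction between time and the group is determined. If it is not significant, it is eliminated from the model". Adjusted means, 95% confidence intervals and p-values come from whichever model remains. That section gives no threshold for the interaction test; 5% is read from section 3.1.

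The rule also reaches the illness-belief items. Section 5.1, Other Outcomes, lists "Brief IPQ single items (difference from baseline (T0) is calculated for 1 month (T2) and 6 months after randomization (T3", and section 5.3 says "Other endpoints will be analysed, depending on the level of scale, as defined for the secondary endpoints".

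**The concern.** Without the interaction, the model holds a single group effect shared by T2 and T3. Adjusted means for one month can still be printed, but the difference between arms at one month is by construction the difference at six months. The plan names a one-month endpoint and then lets a pre-test decide whether a one-month contrast exists.

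A non-significant interaction does not show that the effects are equal. The trial is sized in section 2.3 for a between-group effect of f = 0.118, not for a change in that effect over time.

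What is at stake is the meaning of the reported interval. An effect present only at six months could be reported as an early effect, or an early effect that fades could be diluted.

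**Working it through.** **Is there another one-month contrast in the SAP?**

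- The primary ANCOVA in section 5.3 concerns the T0-to-T3 change only.
- The model under Sensitivity Analyses ("Further for the primary endpoint a multilevel linear model with change from baseline as outcome incorporating the participants as a random term") names group, time point and baseline but no interaction, so it too gives one common group effect.
- The summaries by group and time point are unadjusted and carry no contrast or interval.

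So no other adjusted one-month contrast is specified.

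**Inputs from the SAP.** Three arms 1:1:1 (2.1); 233 analysable per arm, 358 recruited, f = 0.118, 80% power, 35% dropout (2.3); 5% tests and 95% intervals (3.1).

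**Assumed, because the SAP gives no values.** T2-T3 residual correlation ρ = 0.3, 0.5 or 0.7; equal residual SD at both visits, set to 1; complete data; one arm differing. Let g be the gap between that arm's T2 and T3 effects, in SD units.

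**Plan's own figure.** Noncentral F with 2 and 3n − 4 df and noncentrality 3n·f². At n = 233 this is 699 × 0.118² = 9.73, giving power 80.2%; 232 would just suffice. For dropout, 233/0.65 = 358.5. The stated 233 and 358 are reproduced to within one participant per arm. If one arm differs from two equal arms, f = d·√2/3, so d = 0.118 × 3/1.414 = 0.250 SD.

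**Chance that the term is deleted.** The interaction test is a 2-df F test on the T3 − T2 differences, which have variance 2(1 − ρ). Its noncentrality is λ = n·g²/[3(1 − ρ)]. For g = 0.125, n·g² = 233 × 0.015625 = 3.641, so λ = 3.641/2.1, 3.641/1.5 and 3.641/0.9 = 1.73, 2.43 and 4.05. The deletion probability is that of a noncentral F (2 and 696 df) falling below its 5% critical value, 3.01.

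**What is estimated after deletion.** With complete data, the pooled contrast is the average of the T2 and T3 contrasts, so it misses the one-month effect by g/2.

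- One-month SE: √(2/233) = 0.0926.
- Pooled SE: √((1 + ρ)/233) = 0.0747, 0.0802, 0.0854.
- Ratio: √((1 + ρ)/2) = 0.81, 0.87, 0.92.

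Coverage given deletion is Φ(1.96 − b) − Φ(−1.96 − b), with b = (g/2)/pooled SE. For g = 0.125, b = 0.0625 divided by each pooled SE = 0.84, 0.78, 0.73, giving 86.7%, 87.8% and 88.7%.

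**Overall one-month coverage.** Simulated with 40,000 replicates per scenario and 233 per arm; entries are for ρ = 0.3 / 0.5 / 0.7.

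| Gap g (SD) | Term deleted, % | Coverage under the SAP rule, % |
|---|---|---|
| 0 | 95 (the test's level) | 94-95 |
| 0.0625 | 92 / 90 / 87 | 92.4 / 92.9 / 93.3 |
| 0.125 | 80.0 / 73.5 / 58.2 | 87 / 89 / 91 |
| 0.1875 | 60 / 46 / 23 | 83 / 87 / 92 |
| 0.25 | 35.1 / 19.9 / 4.2 | 83-84 / 89-90 / 94 |

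Keeping the term gives 95% throughout. Both feedback arms sharing the effect gives the same results. A graded pattern (none, half, full effect) is somewhat worse, with lowest coverage 79 / 85 / 90%.

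With no one-month effect and a six-month effect of 0.25 SD, the interval for one month wrongly excludes zero in 16 / 11 / 6% of trials, against a nominal 5%.

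With 358 per arm, coverage is 87.9 / 92.8 / 95.0% for effects of 0 at T2 and 0.25 SD at T3, and 85.3 / 87.8 / 91.0% for 0.125 and 0.25 SD.

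**The case against.** The strongest defence is that little hangs on this contrast. Sections 3.1 and 5.3 call the secondary analyses exploratory, both hypotheses in section 1.2 concern six months, and GAD-7, SSS-8 and EQ-5D-5L have T3 only. Testing the interaction and then dropping it is a familiar strategy, and here it was fixed before analysis.

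It can also pay. With no gap, the root mean squared error of the one-month estimate is 0.078 / 0.083 / 0.087 SD under the rule, against about 0.093 with the term kept. At a gap of 0.0625 SD it is 0.085 / 0.089 / 0.093 against 0.093. The rule loses on this measure only from about 0.125 SD upward, half the design effect of 0.25 SD, and the SAP does not say how the effect should change between visits. Averaged over all trials, the bias peaks at only 0.039 / 0.034 / 0.024 SD, because large gaps usually keep the term.

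Finally, the calculation is idealised. Section 3.3 admits participants with a single post-baseline value and section 2.3 expects 35% dropout, so the pooled estimate need not be the simple T2/T3 average.

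All of this stands and limits the weight of the point. It does not remove it. Exploratory status waives multiplicity adjustment; it does not make an interval for a pooled effect into a 95% interval for a listed one-month endpoint. Unbalanced data change the weights and the percentages, but the contrast is still common to both visits.

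**Conclusion.** The concern holds. Under the stated rule, the adjusted one-month PHQ-9 contrast becomes a pooled T2/T3 contrast whenever the interaction test is not significant, and no other part of the SAP restores it. The same applies to the Brief IPQ items.

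On the assumptions above, the lowest one-month coverage with one arm differing is about 83%, 87% and 91% at correlations of 0.3, 0.5 and 0.7. The loss is negligible if the effects are equal, and small if the correlation is high and the gap large. The mechanism is certain; the percentages are illustrative, because the SAP gives neither the correlation nor the expected course of the effect.

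The primary six-month analysis and its error rate are untouched. This should be changed, as a cheap improvement to an exploratory analysis.

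**What to change.** In SAP section 5.3, Analysis of Secondary Endpoints, delete the sentence that removes a non-significant interaction. State instead that, for outcomes measured at both T2 and T3 (PHQ-9 and the Brief IPQ items), the group-by-time term stays in the model whatever its p-value, and that the group contrasts at T2 and at T3 are reported from that model with 95% confidence intervals.

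This changes one sentence and needs no new data, no change in sample size and no change to the primary analysis. The price is precision if the effect truly is constant: the pooled standard error would have been 0.81, 0.87 or 0.92 of the one-month standard error at correlations of 0.3, 0.5 and 0.7.
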